**4. 28-day Vasopressor Free Days**

Vasopressor free days to day 28 are defined as the number of calendar days between day 2 (eligibility starting 48 hours post randomization) and 26 days later that the patient is alive and without the use of vasopressor therapy. We also followed the “last off” method. Patients who died prior to day 28 and those who receive vasopressor therapy for the entire first 28 days are assigned zero vasopressor free days.

**5. 28-day ICU free days**

ICU free days to day 28 are defined as the number of days spent alive out of the ICU to day 28.

**6. 28-day hospital free days**

Hospital free days to day 28 are defined as 28 days minus the number of days from randomization to discharge home. If a patient has not been discharged home prior to study day 28 or dies prior to day 28, hospital free days will be zero. Patients transferred to another hospital or other health care facility will be followed to day 28 to assess this endpoint.

**7. Initiation of mechanical ventilation to day 28**

Patients who receive invasive mechanical ventilation via endotracheal or tracheostomy tube, except those intubated solely for a procedure and extubated within 24 hours, through to study day 28 meet this endpoint. Non-invasive mechanical ventilation will not be included as an outcome. This is a binary outcome.

**8. Initiation of renal replacement to day 28**

Patients who receive (new) renal replacement therapy through day 28 will meet this endpoint. Patients with chronic renal replacement therapy initiated prior to the current sepsis illness will not be eligible to meet this endpoint.

**9. Change in creatinine-based KDIGO stage between baseline and 72 hours**

Renal function will be assessed using the KDIGO staging system (serum creatinine criteria only; not urine output) between baseline and 72 hours to assess for de novo acute kidney injury (AKI) (e.g., meeting criteria for AKI by KDIGO criteria) or worsening AKI (e.g., increasing severity). Due to the potential influence of treatment assignment on urine output, as well as the potential for inaccurate urine output data in patients without indwelling urinary catheters, we will use only the KDIGO creatinine criteria. Patients on chronic renal replacement therapy will not be eligible for this endpoint determination.

**10. Change in SOFA score between baseline and 72 hours**

We will calculate the SOFA score upon enrollment and at 72 hours using clinically available data. If a value is not available at baseline, it will be assumed to be normal. At the 72 hours assessment, if a value is missing then we will carry forward the closest previously known value. If a patient is intubated or heavily sedated at either 0 or 72 hours, the GCS will be omitted when calculating the change in score. If a patient was on renal replacement therapy prior to presentation, then the renal dysfunction component to the SOFA score will be omitted as well.

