1.2 Definitions

Adverse Event: Any untoward medical occurrence associated with the use of a drug or a study procedure, whether or not considered drug related.

Adverse reaction: An adverse reaction means any adverse event caused by a study intervention. An adverse reaction is a subset of all suspected adverse reactions where there is a reason to conclude that the study intervention caused the event.

Assisted Ventilation (or Assisted Breathing): any level of ventilatory support at pressures higher than the unassisted breathing thresholds.

Home: Level of residence or health care facility where the patient was residing prior to hospital admission.

Intention to Treat (ITT): All eligible and consented patients who undergo randomization will be included in the ITT cohort for the purposes of analyzing the primary and secondary study outcomes.

Invasive Mechanical Ventilation: Assisted ventilation delivered by a nasotracheal, orotracheal, or tracheostomy tube.

Legally Authorized Representative: An individual, judicial, or other body authorized under applicable law to consent on behalf of a prospective patient to the patient's participation in the clinical study.

Mortality prior to discharge home before day 90: This primary outcome includes deaths from all causes following randomization in any health care facility prior to discharge home until study day 90. Study subjects still in a health care facility at study day 91 are considered alive for this endpoint.

Funding: National Institutes of Health (National Heart Lung and Blood Institute)

SAEs: Serious Adverse Events Adverse events that are serious and unexpected and have a reasonable possibility that the event was due to a study procedure

Sponsor: The Clinical Coordinating Center at Massachusetts General Hospital

Study day: The day of randomization is study day zero. The next day is study day one etc.

Study hospital: Defined as the hospital where the patient was randomized and enrolled.

Study withdrawal: Defined as permanent withdrawal from study before completion of study activities. If a patient or surrogate requests withdrawal from the study the clinician should seek explicit permission to continue data collection.

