3.6.2 Secondary Outcomes

1. 28-Day Organ Support Free Days

Organ support free days is defined as a patient being alive and without assisted breathing, new renal replacement therapy, or vasopressors (beyond 48 hours). Patients will be followed for use of organ support to death, hospital discharge or study day 27, whichever comes first. Any day that a patient is alive and without organ support will represent days alive and free of organ support. Since there will be a bias in the protocols to place patients on vasopressors in the restrictive group, vasopressor use prior to 48 hours will be excluded from this calculation for both groups.

2. 28-day Ventilator Free Days (VFDs)

VFDs depend on both duration of ventilation and mortality through study day 28. In participants who survive 28 days, VFD is defined as 28 minus duration of ventilation. Duration of ventilation is counted from the first study day of assisted breathing through the last day of assisted breathing provided the last day is prior to day 28. Otherwise, it is counted from the first study day of assisted breathing through day 28. For participants discharged with assisted ventilation (e.g., to LTAC facility) prior to day 28, a phone call will be required to assess ventilator and vital status at day 28. Participants discharged prior to day 28 on unassisted breathing will be assumed to remain on unassisted breathing through day 28. Isolated periods of ventilation briefer than 24 hours for surgical procedures and ventilation solely for sleep disordered breathing do not count towards duration of ventilation. In participants who never require assisted breathing, duration of ventilation is zero. Participants who do not survive 28 days will be assigned zero VFD. VFD is undefined in participants with chronic/home mechanical ventilation (except solely for sleep disordered breathing) and they will be excluded from this analysis.

3. 28-day Renal Replacement Therapy Free Days

Renal replacement free days to day 28 are defined as the number of calendar days between randomization and 28 days later that the patient is alive and without new renal replacement therapy. We also follow the “last off” method. Patients who died prior to day 28 and those who receive renal replacement therapy for the entire first 28 days are assigned zero renal replacement free days.

4. 28-day Vasopressor Free Days

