7.3 Other Assessments and Data Collection

1. Vasopressor use over the hospitalization
2. Assisted ventilation over the hospitalization
3. New renal replacement therapy over the hospitalization
4. Daily fluid administration for the first 7 days
5. Daily fluid outputs (truncated for death or ICU discharge) for the first 7 days
6. Diuretic administration over the first 7 days
7. Clinical laboratory testing results during the first 72 hours post randomization
8. Results of microbiologic testing from samples taken over the first 72 hours after randomization
9. SOFA at hours 0 and 72

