The NHLBI PETAL Network DSMB is appointed by the Director, NHLBI and makes recommendations to the NHLBI Director. The DSMB reviews all protocols for safety following review by an independent NHLBI Protocol Review Committee. The DSMB will consist of members with expertise in acute lung injury, emergency medicine, biostatistics, ethics, and clinical trials. An NHLBI staff member not associated with PETAL will serve as Executive Secretary. Appointment of all members is contingent upon the absence of any conflicts of interest. All the members of the DSMB are voting members. The Principal Investigator and the Medical Monitor of the CCC will be responsible for the preparation of all DSMB and adverse event reports and may review unblinded data. The DSMB will develop a charter and review the protocol and sample consent form during its first meeting. Subsequent DSMB meetings will be scheduled in accordance with the DSMB Charter with the assistance of the CCC. When appropriate, conference calls may be held in place of face-to-face meetings. Recommendations to end, modify, or continue the trial will be prepared by the DSMB executive secretary for review by Director, NHLBI. Recommendations for major changes, such as stopping, will be reviewed by the NHLBI Director and communicated immediately. Other recommendations will be reviewed by the NHLBI director and distributed in writing to the CCC, which will distribute to the PETAL steering committee with instructions for reporting to local IRBs when appropriate.

Details of the NHLBI policies regarding DSMBs can be found at the following URL:

http://www.nhlbi.nih.gov/funding/policies/dsmb_inst.htm

The PETAL Network Steering Committee is comprised of the Principal Investigators and Co-investigators of all the Clinical sites, the CCC, and the NHLBI Project Officer who represents the NHLBI. All sites have two votes and the CCC has one.

C. SOFA Scoring System

Variables	SOFA Score				
	0	1	2	3	4
Coagulation Platelets x 10 ³ /μL	>150	≤150	≤100	≤50	≤20
Liver Bilirubin, mg/dL	<1.2	1.2-1.9	2.0-5.9	6.0-11.9	>11.9
Cardiovascular Hypotension	No hypotension	Mean arterial pressure <70 mmHg	Dop ≤5 or dob (any dose) ‡	Dop >5, epi ≤0.1, or norepi ≤0.1 ‡	Dop >15, epi >0.1, or norepi >0.1 ‡
Renal Creatinine, mg/dL or urine output, ml/d	<1.2	1.2-1.9	2.0-3.4	3.5-4.9 or <500	>4.9 or <200

*Norepi indicates norepinephrine; Dob, dobutamine; Dop, dopamine, Epi, epinephrine.

†Values are with respiratory support.

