### Secondary Outcomes

Continuous secondary outcomes will be compared between treatment groups using a t-test.

Categorical secondary outcomes will be compared between treatment groups using a Chi-square or Fisher's exact test as appropriate to the sparseness of the data.

The analysis is intention to treat and significance testing will be two-tailed at  $\alpha = 0.05$  with no adjustment made for multiple comparisons.

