### Missing Data

Analysis is based on all available data with no imputation of missing data; except in the case of selected derived variables, for example SOFA variables.-

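### Change in SOFA to 72 hours has no rule for death: read literally, carry-forward scores an early death from the last pre-death values, and the plan can also be read as dropping such patients

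*SAP*

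**What the plan says.** The endpoint is item 10 of SAP section 2.2 and of protocol section 3.6.2, worded alike. Two filling rules apply. At baseline: "If a value is not available at baseline, it will be assumed to be normal". Later: "At the 72 hours assessment, if a value is missing then we will carry forward the closest previously known value". The item makes exceptions for sedated or intubated patients and for prior renal replacement, but none for death.

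Three other places decide who is scored and how:

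- SAP section 5, Missing Data, rules out imputation "except in the case of selected derived variables, for example SOFA variables", so the carry-forward stays in force.
- Protocol section 1.2 defines the analysis set for primary and secondary outcomes: "All eligible and consented patients who undergo randomization will be included in the ITT cohort".
- SAP section 5, Secondary Outcomes: "Continuous secondary outcomes will be compared between treatment groups using a t-test".

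Other endpoints do deal with death. Ventilator, renal replacement, vasopressor and hospital free days each assign zero to patients who die before the 28-day mark. In the SHAMROC appendix (protocol Appendix J), death counts as the most extreme poor cognitive or physical outcome.

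**The concern.** A patient who has died by 72 hours has no 72-hour value for any component. If the carry-forward sentence covers that patient, the change score is the last recorded state before death minus baseline. The worst possible course then enters the t-test as moderate worsening, or less. An arm that prevents early deaths gets too little credit on this endpoint, and an arm that causes them is penalised too little.

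The alternative reading comes from SAP section 5, Null Hypothesis, which speaks of outcomes defined only in patients still on study and mentions survivorship bias. On that reading the dead are left out, and the comparison is between groups selected by survival after randomization. The section gives no scoring rule, so an analyst could follow either reading and report a different number.

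The measure also has a second use. Protocol section 7.2 sends changes in SOFA to the DSMB as study process safety data, where muted early deaths are unhelpful.

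**Working it through.** **No plan figure to reproduce.** The documents give no SD, effect size, power or early-death count for SOFA. The only planning inputs used are these:

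- Maximum sample size 2,320 at 1:1 (protocol section 9.1), so 2,320 / 2 = 1,160 per arm. The standard two-proportion formula for 15% against 10.5% with 90% power gives 2,306, so 2,320 is not in dispute.
- Planned relative reduction in mortality: (15 − 10.5) / 15 = 30%. This is borrowed as the assumed cut in early deaths.

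**Assumptions, not in the documents.**

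- Deaths by 72 hours in the higher-mortality arm: d = 3% to 5%. That is 3/15 = 20% to 5/15 = 33% of the planned 15%, or about 35 to 58 patients of 1,160.
- SD of the change under the current rule: 4.
- Gap g between a worst score and the carried score: 4-8 points if the carried value is a late, already bad one; 12-18 points if it is closer to baseline.

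**Formulas.**

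- Understatement of mean worsening in the higher-mortality arm: d × g.
- Between-arm shift when the other arm has 30% fewer early deaths: 0.30 × d × g.
- Standard error under the current rule: 4 × √(2/1160) = 0.166.
- Scoring deaths as worst also widens the spread. If the carried change is unrelated to death, and the same d is used in both arms for simplicity, the SD becomes √(16 + d(1 − d)g²), and the SE is that times √(2/1160) = 0.0415.

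| d | g | d × g | Shift | Widened SD | Widened SE | Shift / SE |
|---|---|---|---|---|---|---|
| 3% | 4 | 0.12 | 0.036 | 4.06 | 0.168 | 0.2 |
| 5% | 8 | 0.40 | 0.12 | 4.36 | 0.181 | 0.7 |
| 3% | 12 | 0.36 | 0.108 | 4.49 | 0.187 | 0.6 |
| 5% | 18 | 0.90 | 0.27 | 5.60 | 0.233 | 1.2 |

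Points serve here only to size the issue. A rank test needs no numerical score for death.

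**Vasopressor points from the protocol window.** For organ support free days, "vasopressor use prior to 48 hours will be excluded from this calculation for both groups", because the protocols favour vasopressors in the restrictive arm. SOFA has no such exclusion. Protocol Appendix C gives 1 point for MAP below 70 and 3 points for "Dop >5, epi ≤0.1, or norepi ≤0.1", with 4 above that dose. Suppose early mortality is equal, vasopressor use at the last record differs by 20-40 percentage points between arms, and each such record adds 2-4 points. With 3% early deaths, the low end is 0.03 × 0.20 × 2 = 0.012 points between arms. With 7.5% (half of the planned 15%), the high end is 0.075 × 0.40 × 4 = 0.12 points.

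**The case against.** The strongest reply is that nothing in the plan says outright that the dead are scored by carry-forward. The sentence concerns a value missing at the 72-hour assessment, and one may argue that a dead patient has no such assessment. That stands as far as it goes: the literal reading is an inference from three passages taken together. It does not remove the problem, because leaving the dead out is not written down either.

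A reader might infer that early deaths are scored as unchanged, since protocol section 7.3 lists "SOFA at hours 0 and 72". The documents do not support that as the usual case. The same section collects laboratory results through 72 hours, and Appendix F schedules GCS and vasopressor use on days 1 to 3, with laboratory results when available. Many early deaths would carry a later and often worse value. A zero change for a component needs a patient with no value after baseline, which is an extreme. On a 24-point scale, the 12-18 point gap implies a carried score of 6 to 12 and sits near that extreme.

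A reader might also infer that carried-forward vasopressor points seriously distort the endpoint. The effect is small in the calculation above. It raises the scores of those who die, opposite to the understatement, and shrinks where the patient was already on a vasopressor at enrollment, which the inclusion criteria allow.

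It is fair, too, that this is one of many secondary endpoints tested without multiplicity adjustment, that mortality is captured elsewhere, and that treating death as worst is a choice of estimand. Under a null of no effect on anyone, the SAP's claim of a correct error rate is not challenged. The trial's hypothesis, however, is that mortality differs.

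**Conclusion.** The concern holds as a gap with a consequence. No rule for death is written, the literal rule understates the worst outcome, and a second reading gives a different result. This departs from the plan's own practice in the four free-day endpoints with an explicit rule.

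Under the stated assumptions the between-arm shift is about 0.04-0.12 points with a carried score close to the worst, and 0.11-0.27 points with one far from it. The latter is about 0.6-1.2 standard errors once the wider spread is counted. Dividing by the unwidened 0.166 would give 0.65-1.6, which overstates it. A shift in the upper part of the range could affect a test at 0.05; one in the lower part would rarely matter. Which applies cannot be settled from the documents. The point merits correction but does not touch the primary analysis.

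**What to change.** In SAP section 2.2 item 10, and in the protocol item to match:

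1. Limit carry-forward to patients alive at 72 hours, including those discharged alive before then.
2. Rank death before 72 hours below all survivors and compare arms with a rank test in place of the t-test for this endpoint.
3. Add a survivors-only analysis as sensitivity, reported with the number of deaths before 72 hours in each arm.
4. As a minor sensitivity analysis, repeat the comparison without cardiovascular values carried forward from the first 48 hours.

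The cost is a few sentences in the SAP and a little programming. Timing of death is already needed for the Kaplan-Meier primary analysis; the text should say whether 72 hours is judged by clock time or by study day. The downside is that the main result reads as a combined death and organ-dysfunction measure and should be labelled so.

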**11. 90-day all-cause mortality**

We will contact patients at day 90 to ascertain their survival status. This will be done by telephone contact with the patient or family members as well as a review of medical records and publicly available data sources. We will use the national death index as a final check for patient with whom we are unable to confirm their vital status through other means.

**12. Development of ARDS within 7 days**

We will determine the presence and severity of ARDS for each day of mechanical ventilation to day 7 using the following approach: for each ventilator day, if an ABG is available between 2:00 AM and 8:00 AM, measure P/F (PaO2, FiO2 and PEEP) for all ABGs during this time window daily to day 7. Or, for ventilator days that no ABG available between 2:00 AM and 8:00 AM, determine lowest imputed P/F from measured S/F (SpO2, FiO2, and PEEP).

For participants with P/F <300 or imputed P/F <300, FiO2 ≥40%, and PEEP ≥5 cm H2O, determine if hypoxemia is valid, acute, and not fully explained by CHF or fluid overload. If yes, local investigators will review the first CXR (or CT) performed on each ventilated day with valid P/F or imputed P/F <300 (to day 7). If no chest imaging studies are present that day, site investigators may review available imaging one day before or after to determine if ARDS imaging criteria met. ARDS imaging criteria are met if the images are consistent with ARDS (bilateral opacities not fully explained by effusions, lobar/lung collapse, or nodules). If equivocal, the reviewing investigator will adjudicate with additional investigators.

### 13. Supraventricular/ventricular tachycardia (SVT/VT) or new onset atrial fibrillation/flutter (AF) to day 28

The occurrence of one or more episodes (sustained for more than 1 minute for SVT and AF, > 15 seconds for VT) during through day 28 will be recorded.

#### 2.3 Process of Care Metrics

1. Total intravenous fluids administered over first 6 hours after randomization
2. The total amount of intravenous fluids or blood products of any type administered from pre-randomization to 6 hours after randomization.
3. Total intravenous fluids administered over 24 hours after randomization
4. The total amount of intravenous fluids or blood products of any type administered from pre-randomization to 24 hours after randomization.
5. Proportion receiving vasopressors and timing of vasopressor initiation within 24-hour study period
  - a. Proportion of patients receiving vasopressors within 24 hours will be calculated. Additionally, among patients who received vasopressors, the duration of time elapsed from randomization until the time of initiation of vasopressor medications within 24-hour protocol period will be recorded.
6. Total fluids administered prior to initiation of vasopressors
  - a. This process of care metric will assess the amount of fluids administered prior to the first receipt of vasopressors. (patients on vasopressors prior to randomization excluded from this metric)
7. Proportion of patients receiving two or more liters of fluid in the first six hours.
8. Administration of first and second liter of fluid infusion in liberal arm
  - a. This process of care metric will summarize frequency of use of second liter and reasons for use or declining use.

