3.6.3 Process of Care Metrics

1. Total intravenous fluids administered over first 6 hours after randomization
2. The total amount of intravenous fluids or blood products of any type administered from pre-randomization to 6 hours after randomization.
3. Total intravenous fluids administered over 24 hours after randomization
4. The total amount of intravenous fluids or blood products of any type administered from pre-randomization to 24 hours after randomization.
5. Proportion receiving vasopressors and timing of vasopressor initiation within 24-hour study period

- a. Proportion of patients receiving vasopressors within 24 hours will be calculated. Additionally, among patients who received vasopressors, the duration of time elapsed from randomization until the time of initiation of vasopressor medications within 24-hour protocol period will be recorded.
6. Total fluids administered prior to initiation of vasopressors
 - a. This process of care metric will assess the amount of fluids administered prior to the first receipt of vasopressors. (patients on vasopressors prior to randomization excluded from this metric)

We will use a bedside flow-sheet as a data collection instrument to record fluid and vasopressor administration, with the indications for administration, during the 24-hour protocol period. This will detail the delivery of the study interventions and assess protocol compliance. The data will be reported to the protocol oversight committee (and disseminated to the sites as protocol compliance metrics) as aggregate per-arm data in a blinded fashion (e.g. descriptive numbers only without an “n” or any indication of outcome or clinical status). This will occur at the 100, 200, and 300 patient data completion marks as described in the feasibility evaluation phase (Section 8). After the feasibility evaluation phase, we will perform a simplified data collection of summary fluid and vasopressor administration during the 24-hour treatment period and the data will be distributed after the first 10 patients for any new site, and then quarterly, to allow treatment protocol adherence monitoring. Any site with deficient compliance and/or separation of treatment arms after the initial 10 patients or during the quarterly reports may receive re-education and/or be asked to cease enrollment.

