## 1.9 Secondary Endpoints

1. 28-day organ support free days (alive and without mechanical ventilation, new renal replacement or vasopressors; vasopressors prior to 48 hours excluded)
2. 28-day ventilator free days
3. 28-day renal replacement free days (new renal replacement therapy)
4. 28-day vasopressor free days (vasopressors prior to 48 hours excluded)
5. 28-day ICU free days
6. 28-day hospital free days to discharge home
7. Initiation of mechanical ventilation to day 28
8. Initiation of renal replacement therapy to day 28
9. Change in creatinine-based KDIGO stage between baseline and 72 hours
10. Change in SOFA score between baseline and 72 hours
11. 90-day all-cause mortality
12. Development of ARDS within 7 days
13. New onset atrial or ventricular arrhythmia to day 28
14. Additional secondary safety endpoints:
  - a. New intubation through day seven
  - b. New mechanical ventilation through day seven
  - c. Ventricular arrhythmias in first 24 hours
  - d. New renal replacement therapy through day seven
  - e. New ARDS through day seven
  - f. ICU admission through day seven
  - g. Central venous line insertion through day three
  - h. Vasopressor infusion through peripheral venous catheter
  - i. Line complications of central venous catheter placement
  - j. Line complications
  - k. More than three line complications among patients with a line complication
  - l. Site extravasation to day 28 from peripheral venous catheter infusion
  - m. New ventilation and oxygen use in first 24 hours
  - n. Adverse events

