### Process of Care Metrics

The analysis of the process of care metrics will be similar to that of the secondary outcomes.

The analysis is intention to treat and significance testing will be two-tailed at  $\alpha = 0.05$  with no adjustment made for multiple comparisons.

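### Time to vasopressor start is tested only among vasopressor recipients, so a test labelled intention to treat does not compare randomized groups and may misstate separation in either direction

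*SAP*

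**What the plan says.** SAP 2.3 item 5 has two parts. The first covers everyone: "Proportion of patients receiving vasopressors within 24 hours will be calculated". The second is timing, measured "among patients who received vasopressors, the duration of time elapsed from randomization until the time of initiation of vasopressor medications" within the 24-hour protocol period. Protocol 3.6.3 defines the metric in the same way.

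SAP 5 sets the analysis: "The analysis of the process of care metrics will be similar to that of the secondary outcomes". For a continuous measure this leads to the Secondary Outcomes rule: "Continuous secondary outcomes will be compared between treatment groups using a t-test". The label is explicit: "The analysis is intention to treat and significance testing will be two-tailed", at 0.05 and without multiplicity adjustment.

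Item 6 concerns fluid before vasopressors: "This process of care metric will assess the amount of fluids administered prior to the first receipt of vasopressors". Its only stated restriction, in both documents, is "patients on vasopressors prior to randomization excluded from this metric". Neither document says what value a patient who never starts a vasopressor takes.

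Three other places bear on who becomes a recipient:
- Protocol 5.1 has the restrictive arm start vasopressors at MAP below 65 or SBP below 90 mmHg.
- Protocol 5.2 answers the same pressures in the liberal arm with fluid and recommends vasopressors on rescue criteria, one of which is SBP below 70 or MAP below 50 mmHg for at least 5 minutes.
- SAP 2.2 item 1 acknowledges that the protocols favour vasopressor use in the restrictive group, and for that reason leaves out vasopressor use before 48 hours.

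**The concern.** A comparison is intention to treat when it keeps the groups that randomization formed. Item 5 timing keeps only patients who went on to receive a vasopressor, and the arms are designed to differ in who that is. Recipients under an early-start strategy and recipients under a rescue strategy need not be alike in severity. Patients who avoided vasopressors altogether, which is one form that separation takes, drop out of the timing comparison.

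Protocol 2.10 and SAP 1.10 list vasopressor timing and fluid before vasopressors among the measures of whether care was altered as intended. A timing difference that is too small, too large or of the wrong sign would mislead a reader about delivery of the strategies, and a p-value labelled intention to treat would lend it authority it lacks.

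Two definitional gaps add to this. If item 6 is computed only where a first vasopressor exists, it inherits the same selection. And Protocol 4.2 criterion 3 admits patients already receiving a vasopressor infusion. Item 6 removes them; item 5 does not, although time from randomization to initiation is undefined for them.

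**Working it through.** The plan states no expected value for item 5 timing or item 6, so there is no plan figure to reproduce. Uptake and start times below are assumptions, varied to show the range.

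**Step 1. Two contrasts.** Let p be the proportion starting within 24 h and m the mean start time among starters (R restrictive, L liberal).
- Recipients-only difference: m_L − m_R.
- All-patient difference: mean time before first start over 24 h is p·m + (1 − p)·24, with never-starters counted at 24 h. Take L minus R. (Deaths are ignored here.)

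**Step 2. Numbers.**

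| p_R, m_R | p_L, m_L | Recipients only | All patients |
|---|---|---|---|
| 60%, 1 h | 35%, 5 h | 4.0 h | 17.35 − 10.2 = 7.15 (7.2 h) |
| 60%, 1 h | 35%, 8 h | 7.0 h | 18.4 − 10.2 = 8.2 h |
| 60%, 1 h | 35%, 10 h | 9.0 h | 19.1 − 10.2 = 8.9 h |
| 60%, 2 h | 40%, 5 h | 3.0 h | 16.4 − 10.8 = 5.6 h |
| 60%, 2 h | 40%, 2 h | 0 h | 15.2 − 10.8 = 4.4 h |
| 60%, 2 h | 60%, 5 h | 3.0 h | 12.6 − 10.8 = 1.8 h |

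First row in full: restrictive 0.60 × 1 + 0.40 × 24 = 10.2; liberal 0.35 × 5 + 0.65 × 24 = 17.35.

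The recipients-only figure is smaller in four rows, about equal in one (9.0 against 8.9 h) and larger in the last. For p_R = 60% and means of 2 and 5 h, the crossover solves 24 − 19·p_L − 10.8 = 3, so p_L = 10.2/19, about 54%. Below that liberal uptake the metric understates; above it, it overstates.

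**Step 3. Are the compared groups alike?** In a simulation where an assumed latent severity drives both receipt and speed of start, with 60% and 40% uptake, recipients averaged 0.51 SD above the mean in the restrictive arm and 0.77 SD in the liberal arm. With no true delay at a given severity, recipients-only timing differed by −0.4 h (liberal earlier; expected t about −2.0 at 1,160 per arm), while the all-patient difference was +4.0 h. The sign can therefore reverse. With identical arms both differences were zero, to within simulation error.

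**Step 4. Item 6 if never-starters were dropped.** Take 60% and 40% uptake, recipients at 0.5 and 3.0 L, non-recipients at 1.0 and 2.0 L. Recipients only: 2.5 L. All patients: (0.4 × 3.0 + 0.6 × 2.0) − (0.6 × 0.5 + 0.4 × 1.0) = 2.4 − 0.7 = 1.7 L. A simulated case with both uptake and delay differing went the other way (1.36 against 1.97 L). Here too the direction is not fixed.

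**The case against.** The strongest reply is that the proportion started plus timing among starters is a conventional two-part description, and item 5 reports both. Much of the gap between the two columns above is the uptake difference, which the proportion already shows. That stands as a defence of reporting recipients-only timing. It does not defend a t-test of it under an intention-to-treat label.

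SAP 5, Null Hypothesis, concedes case-mix imbalance for outcomes defined only in patients still on study, and claims correct type I error under a global null of no effect on anyone. The claim is consistent with the identical-arms result in Step 3. But the section speaks of recovery and survivorship, and its null cannot be expected for a metric that the protocol is built to change.

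Three stronger readings are tempting and are not supported:
- *Separation will be understated, and mostly lost.* Constant start hazards with 60% and 35% uptake give 1.0 h among recipients against 3.8 h in all patients. That model puts the mean restrictive start among recipients at 10.2 h. It fits poorly with the 60-minute start standard in Protocol 8.2 and with the requirement in exclusion criterion 14 of current hypotension or vasopressor use. Front-loaded starts with the same uptake give the first three rows of the table.
- *Item 6 is limited to recipients.* Its text does not say so; it leaves never-starters undefined.
- *These two metrics decide how a null mortality result is read.* No section says this. Other process metrics measure fluid without restriction to recipients. The separation guidelines in Protocol 8.3 use fluid at 6 and 24 h and mean time of vasopressor use, and neither item 5 timing nor item 6.

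**Conclusion.** The point holds in a limited form. Item 5 timing is, on its own wording, tested in a subset chosen by a post-randomization event that the arm drives, so the intention-to-treat label does not fit. This rests on the text alone.

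The size and direction rest on assumed uptake and timing. Understatement is likely if liberal uptake is clearly lower, but near-agreement, overstatement and a sign reversal all occur under plausible inputs. The defensible statement is that the metric may misstate separation.

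Item 6 is ambiguous for never-starters, and item 5 is silent on patients already on a vasopressor. The latter is a definitional gap and not arm-driven selection, because that status precedes randomization.

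The reach is confined to process metrics. The primary analysis and the feasibility separation guidelines are untouched. This should be corrected, but it does not threaten the main result.

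**What to change.** Amend SAP 2.3 and the Process of Care Metrics paragraph of SAP 5. In all randomized patients not on a vasopressor at randomization:
1. Compare the cumulative incidence of vasopressor start to 24 h, with death as a competing event.
2. Compare mean vasopressor-free time before first start over 24 h, counting never-starters at 24 h and stating the rule for deaths within that window.
3. Define item 6 as fluid given up to first vasopressor or 24 h, whichever comes first.

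Show patients on a vasopressor at randomization separately. Keep timing among recipients as a descriptive summary, with no p-value and no intention-to-treat label.

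The cost is SAP wording and modest programming; nothing in treatment changes. Protocol 7.2 collects fluid and vasopressor timing, and SAP 4 and Protocol Appendix F cover vasopressor use at baseline. One check is needed: Protocol 3.6.3 moves to simplified summary collection after the feasibility phase. The team should confirm that the simplified form keeps the time of first vasopressor and the fluid given up to it. Item 6 as planned already needs both.
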